4.2.3 Use of analysis set

The FAS population will be used for both of efficacy (primary objectives and secondary objectives) and safety evaluation and the PPS will only be used for the efficacy (i.e. secondary objectives) evaluations.

4.3 Definition of Baseline

Baseline measurement is defined as the latest measurement prior to first dose of IMP.

4.4 Summary Statistics

In general, all data collected will be presented with summary statistics and given in patient data listings. Summary statistics will include at least number of patients, mean, standard deviation, median, minimum and maximum for continuous data and frequency and percentage for categorical data. Table with summary statistics will be divided by treatment group and dose group, and visit where applicable. Patient data listings will be sorted by treatment, subject and timing of assessments.

4.5 Significance Level

The estimated intervention difference will be presented by LSMeans and a 95% confidence interval.

4.6 Multiple Comparisons/Multiplicity

All statistical significant findings need to be interpreted from a medical perspective and judged as clinical relevant or not and therefore no adjustment for multiplicity will be performed.

4.7 Handling of Drop-outs, Missing Data and Outliers

Outliers will be included in summary tables and listings, and will not be handled separately in any analyses. No imputation of data will be performed.

4.8 Adjustment for Covariates

History of UTIs and age will be used as covariates in the analysis of mean number of UTIs. Sexual activity will only be used as a covariate in the analysis if it is possible.

4.9 Multicentre Studies

No adjustment for centre will be applied, since this will not be considered as a multi-centre study.

4.10 Examination of Subgroups

Will be discussed with the client.

4.11 Blind Review

Not applicable.

4.12 Deriving of confirmed and unique UTI

Definitions of confirmed UTI – If a subject have at least one of three statements:

- A total number of symptoms ≥ 2
- A positive urine test registered at site
- A positive test, self-reported

Definitions of unique UTI – If a subject have no confirmed UTIs within 14 days prior to the current confirmed UTI and have at least one of two statements:

- Confirmed UTI registered at site
- Confirmed UTI, self-reported and no confirmed self-reported UTIs within 14 days prior to the UTI (only applied to self-reported UTIs, since UTIs registered at site are assigned the date of telephone contact and not the date of the actual UTI)

Assigning dates to confirmed UTIs reported by site personnel: Date of previous telephone contact used if date is ≤ 14 days prior to registering in the UTI log. In case of later reporting of UTIs, the closest unmatched event date with indication of UTI prior to registration is used as date.

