## 7 INTRODUCTION

### 7.1 Project background

Urinary tract infections (UTIs) are the most common bacterial infections in women, with about 50% of women experiencing at least one UTI in their lifetime . Studies have shown that an UTI leads to an average of 1.2 days off work  and the Swedish Medical Products Agency estimates that, in Sweden, UTI cost 254 million SEK annually . UTIs are usually categorized by infection site and can additionally be classified according to whether they are uncomplicated (occurring in the normal urinary tract of immunocompetent individuals, usually young healthy non-pregnant women) or complicated (occurring in individuals of all ages and sexes that are immunocompromised or have genitourinary tracts with structural or functional abnormalities, including urethral catheterisation) .

Most UTIs are acute uncomplicated cystitis caused by *E. coli* (86%), a gram-negative bacterium that is the major source of domestic and hospital infections . Identifiers of acute uncomplicated cystitis are frequency (frequent voiding of urine), urgency (the urge to void immediately), and dysuria (pain in voiding and the absence of both fever combined with flank pain and unusual vaginal discharge) in an immunocompetent woman of childbearing age who has no comorbidities or urological abnormalities . Sometimes haematuria can occur; suprapubic discomfort is less common.

From an epidemiological point of view, infections of the urinary tract and bladder are more common in women than in men . About 4% of women in early adulthood experience bacteriuria and this incidence increases by about 1% to 2% per decade of age . The prevalence of bacteriuria in hospitalized patients increases. In contrast, patients presenting typical UTI symptoms combined with vaginal discharge or irritation have a decreased risk of an uncomplicated UTI . Most uropathogens originate in the rectal flora and enter the bladder via the urethra with an interim phase of periurethral and vaginal colonization, and sometimes they may reach the kidneys .

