## **12.4 Efficacy assessments**

### **12.4.1 Signs of recurrent UTI**

At the monthly assessments, the subjects will be asked to answer pre-defined questions regarding UTI symptoms: frequency (frequent voiding of urine), urgency (the urge to void immediately), and dysuria (pain in voiding and the absence of both fever combined with flank pain and unusual vaginal discharge). If two out of three symptoms are present a UTI is confirmed. If only one symptom is present the subject will perform a nitrite/Leu urine test at home, preferably on urine retained in the bladder for approximately 3 hrs. If the test is positive (one of two analyses), a UTI is confirmed and the subject is recommended to contact the health care system for consultation regarding antibiotic treatment.

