At the monthly assessments (video-call/phone-call or visit), the subject will be asked to answer predefined questions regarding symptoms (frequency, urgency and dysuria). If two out of three symptoms are present a UTI is confirmed. If only one symptom is present the subject will perform a niture/Leu urine test at home, preferably on urine retained in the bladder for approximately 3 hrs. If the test is positive (one of two analyses), a UTI is confirmed and the subject is recommended to contact the health care system for consultation regarding antibiotic treatment. Information on AEs, concomitant medications, use of restricted products, pregnancy, and compliance with instructions for IP intake will be collected.

An electronic diary will be used by the subject during the study period for recording of occurrence of UTI symptoms and sexual activity (frequency of intercourse, new partner, use of condom with spermicide).

The monthly follow-up assessment after six months will be the final study assessment. Number of empty sachets and any unused IP will be reported to CTC AB by the subject and documented by site staff on the IP accountability list.

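### SAP 4.12 lets a positive test alone confirm a UTI, whereas Protocol 12.4.1 and SAP 3.5 require one symptom as well

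*SAP*

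**What the plan says.** **Protocol 12.4.1** (also the synopsis and 9.1) sets a sequence. The symptom questions on frequency, urgency and dysuria come first, and two of the three confirm a UTI. The test belongs to the next branch: "If only one symptom is present the subject will perform a nitrite/Leu urine test at home". Within that branch, "If the test is positive (one of two analyses), a UTI is confirmed". There is no route to confirmation with no symptom.

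**SAP 3.5** repeats the sequence: "If only one symptom is present the subject will perform a niture/Leu urine test at home".

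**SAP 4.12**, the section from which the endpoint will be programmed, uses a different rule: "If a subject have at least one of three statements". The three are:
- "A total number of symptoms ≥ 2"
- "A positive urine test registered at site"
- "A positive test, self-reported"

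The last two carry no symptom condition and do not say which test is meant. A confirmed UTI is then unique if no other was confirmed in the preceding 14 days.

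**SAP 7.1 and 7.2.1** build the primary count, the two three-month counts, time to first relapse and the relapse proportions on confirmed UTIs. **SAP 7.1.2, 7.1.3, 7.2.4 and 7.2.5** plan no sensitivity or supplementary analyses. **SAP section 8** records the definition of confirmed and unique UTI as an addition to the protocol. It does not mention the symptom condition.

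**The concern.** The event behind every efficacy endpoint has two definitions, one of them at odds with another section of the same SAP. They differ in one case: a woman with no symptoms and a positive test. The protocol does not count her and SAP 4.12 does. The case is possible because women with recurrent UTI receive test kits at randomization, and the third alternative accepts whatever positive result they report.

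If such results enter the data, they are not the clinical event named in the objective. Their number would depend partly on how often a woman chooses to test. The 14-day rule would not remove them, since it screens for repeats and not for symptoms. With no sensitivity analysis planned, the report would not show whether they mattered. A reader of SAP section 8 would also not learn that the rule had been loosened.

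**Working it through.** **1. The two rules side by side**

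| Symptoms | Test | Protocol 12.4.1 and SAP 3.5 | SAP 4.12 |
|---|---|---|---|
| 2 or 3 | any | confirmed | confirmed |
| 1 | positive | confirmed | confirmed |
| 1 | negative or none | not confirmed | not confirmed |
| 0 | positive | no route to confirmation | confirmed |
| 0 | negative or none | not confirmed | not confirmed |

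Only the fourth row differs. If tests are done only after one symptom, that row is empty and the counts are identical.

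**2. The plan's own sample size** (Protocol 16.2; SAP 3.4). Inputs: means 0.75 and 1.35, difference 0.60, SD 1.15, two-sided 5%, power 80%, 1:1.
- Standardized difference: 0.60 / 1.15 = 0.522.
- The two-sample t-test needs 58.6 per arm, so 59 per arm and 118 in total. This matches the stated 118, and power at 59 per arm is 80.2%.
- 118 / 0.85 = 138.8, so 139, or 140 with equal arms. This matches the stated 140.

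The sample size is not in dispute.

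**3. Effect on the primary comparison (illustration only).** Let f be the number of symptom-free positives counted per woman over six months. Assume that f is the same in both arms and that these events are Poisson and independent of true UTIs. The documents give no value for f.
- Difference in means: (1.35 + f) − (0.75 + f) = 0.60, unchanged.
- SD: √(1.15² + f) = √(1.3225 + f).

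| f (assumed) | SD | Power, 59 per arm | Evaluable N for 80% power |
|---|---|---|---|
| 0 | 1.150 | 80.2% | 118 |
| 0.05 | √1.3725 = 1.172 | 78.8% | 122 |
| 0.10 | √1.4225 = 1.193 | 77.3% | 128 |
| 0.24 | √1.5625 = 1.250 | 73.4% | 140 |

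The value 0.24 equals 6 monthly tests × 4%, but it is a stress value and not an estimate. The background statement in Protocol 7.1, "About 4% of women in early adulthood experience bacteriuria", describes a share of women and not the chance that one strip reads positive.

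**4. Effect on the other endpoints, same assumptions**
- Relapse proportion: the probability of no event is multiplied by e^(−f) in each arm, so the between-arm difference in proportions shrinks by that factor. For f = 0.05 it is 0.95, and for f = 0.24 it is 0.79.
- Hazard ratio: adding a constant hazard c to both arms gives (h₁ + c)/(h₀ + c), which lies closer to 1 than h₁/h₀.

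**The case against.** The strongest reply is that data collection already applies the missing condition. Symptom questions come first at each call, and SAP 3.5 keeps that order. Protocol 12.6 says that no clinical assessments are made even at a physical visit, so a test registered at site is most naturally a result given during a symptom-first call. The diary is described as recording symptoms and sexual activity, and routine testing without symptoms is not described anywhere. This stands as far as it goes: the documents do not show that any symptom-free positive was recorded. It does not settle which rule governs. A derivation is programmed from its literal wording, and if the reply is right, restoring the condition changes the count only where a symptom went unrecorded.

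Three further points stand and limit the claim:
- No number of unprompted tests can be taken from the documents, and 4% is a prevalence. Persistent bacteriuria would also cluster within women, so the Poisson variance is only a convenience.
- The primary analysis is an ANCOVA difference in means, and neither document plans a rate ratio. A reader might infer that the primary effect is biased towards zero, but equal additions to both arms leave it unchanged.
- SAP section 8 does list the definition among the adjustments to the protocol. A reader might infer that the change was hidden. What is missing is narrower: a statement that the symptom condition is gone.

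The objection that requiring a symptom could remove real UTIs is also fair. SAP 4.12 notes that site-registered UTIs carry the date of the telephone contact, so linking symptom to test needs a window, and SAP 4.7 allows no imputation. This shapes the repair but does not remove the need for it.

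**Conclusion.** The contradiction is certain on the text. SAP 4.12 permits a UTI to be confirmed without any symptom, and Protocol 12.4.1 and SAP 3.5 do not. It reaches the primary endpoint and every secondary UTI endpoint, and no planned analysis would expose it.

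Its numerical effect cannot be known from the documents and may be nil. If symptom-free positives are equally frequent in the two arms, the primary difference is unbiased but less precise, and relapse proportions and the hazard ratio are attenuated. At an assumed 0.05 to 0.24 extra independent Poisson events per woman, power at 59 per arm would be about 79% to 73% instead of 80%. If their frequency differed between arms, the direction of the effect would be unknown.

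A reader might infer that asymptomatic positives are already inflating the count, or that a large loss of power is established. The documents support neither. The case for correction rests on two incompatible definitions of the primary event and not on the illustrated power.

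**What to change.** 1. In SAP 4.12, replace the two test alternatives with one: at least one symptom (frequency, urgency or dysuria) recorded at the same contact, or in the diary within a pre-stated window of the test, **and** a positive nitrite or leucocyte result, site-registered or self-reported. Fix the window before unblinding.
2. Use this definition for the primary endpoint and all secondary UTI endpoints.
3. List positive tests without a recorded symptom by arm, and add a sensitivity analysis that counts them. Amend SAP 7.1.2 and 7.2.4, which now plan none.
4. State in SAP section 8 how the derivation relates to the protocol's rule, including the symptom condition and the matching window.

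The cost is modest: SAP wording, a matching rule and one extra run of the efficacy analyses. No new data are needed, since symptoms are already collected at the calls and in the diary. The downside is that some real UTIs whose symptom was never recorded will leave the main count, which is why the sensitivity analysis is needed.

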**Diagnosis and main eligibility criteria**

Female subjects 18-50 years of age with recurrent UTI and currently on antibiotic treatment for UTI will be considered for participation in the study. Recurrent UTI is defined as occurrence of at least two UTIs during the last six months or at least three UTIs during the last 12 months with a minimum period of two weeks between episodes, unless there is a urinary culture confirming two different pathogens.

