The main pharmacological treatments of cystitis usually involve the use of antibiotics, in particular pivmecillinam, nitrofurantoin or trimethoprim . Quinolones (such as ciprofloxacin and levofloxacin), fosfomycin, second-generation and third-generation cephalosporins, and b-lactam antibiotics associated with b-lactamase inhibitors  may also be used. Because of the formation of bacterial biofilms, unfortunately, the results of antibiotic treatment are often not satisfying. In fact, the infection is not always eradicated and bacteriuria and recurrences may persist . Additionally, the inadequate use of antibiotics in terms of type and duration has been a common practice, generating a continuous increase in bacterial resistance and diverse complications associated to with this indiscriminate use .

As alternatives or in addition to traditional treatments, there are some natural ingredients with a recognized effectiveness in counteracting the onset, persistence, or propagation of a UTI caused by *E. coli*. One example is the use of a dry extract of cranberry (*Vaccinium macrocarpon*), which is able to establish a natural physical-mechanical contrast against the adhesion of *E. coli* to the surface of the epithelial cells of the bladder and urinary tract . Its main activity is related to the proanthocyanidin (PAC) fraction containing oligomers that compete with the adhesions located on type-P fimbriae (FimH, mannose-sensitive) used by *E. coli* to mediate its anchorage to the epithelial cells . The profile of cranberry bioactives is distinct from that of other berry fruits, as they are rich in A-type PACs in contrast to the B-

type PACs present in most other fruit. However, clinical studies of prevention of UTI using cranberry substances are contradictory (as reviewed by Liska, et al 2016).

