The subjects will be contacted by study staff 1-3 days after randomization to confirm that first IP dose has been taken.

At the monthly assessments (video-call/phone-call or visit), the subject will be asked to answer pre-defined questions regarding symptoms (frequency, urgency and dysuria). If two out of three symptoms are present a UTI is confirmed. If only one symptom is present the subject will perform a niture/Leu urine test at home, preferably on urine retained in the bladder for approximately 3 hrs. If the test is positive (one of two analyses), a UTI is confirmed and the subject is recommended to contact the health care system for consultation regarding antibiotic treatment. Information on AEs, concomitant medications, use of restricted products, pregnancy, and compliance with instructions for IP intake will be collected.

An electronic diary will be used by the subject during the study period for recording of occurrence of UTI symptoms and sexual activity (frequency of intercourse, new partner, use of condom with spermicide).

The monthly follow-up assessment after six months will be the final study assessment. Number of empty sachets and any unused IP will be reported to CTC AB by the subject and documented by site staff on the IP accountability list.

The overall study design is shown in Figure 9.1. Assessments will be performed as described in Table 9.1. Each assessment is further described in Section 12.

[figure not shown]

Figure 9.1 Study Flow-chart

*Table 9.1 Schedule of events*

	Screen/ Random.	Intervention period				Follow-up		
		1 st dose	2	3	4	5	6	7
Assessment number	1	1	30±7	60±7	90±7	120±7	150±7	180±7
Day	-10 to 0	1	30±7	60±7	90±7	120±7	150±7	180±7
Informed consent	X							
Demographics	X							
Weight and height information	X							
Medical/surgical history	X							
UTI history	X							
Medication/product history	X							
Inclusion/exclusion criteria	X							
Randomization	X							
IP distribution triggered	X							
Confirmation of IP first dose call	X 							
IP intake		X						
Signs of recurrent UTI		X	X	X	X	X	X	X
AE reporting		X	X	X	X	X	X	X
Pregnancy information	X	X	X	X	X	X	X	X
Diary recordings (ViedocMe TM ) 		X						
Concomitant medications/products 			X	X	X	X	X	X

 1-3 days after randomization

 Information on sexual activity and signs of recurrent UTI.

 See Section 10.6 for restricted products.

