### 10.4 Inclusion criteria

For inclusion in the study, subjects must fulfil the following criteria:

1. Willing and able to give informed consent for participation in the study.
2. Woman aged 18-50 years old, both inclusive, at screening.
3. Body Mass Index (BMI)  $\geq 18$  at screening.
4. Recurrent UTI, otherwise healthy. Recurrent UTI is defined as occurrence of at least two UTIs during the last six months or at least three UTIs during the last 12 months with a minimum period of two weeks between episodes, unless there is urinary culture confirming two different pathogens.
5. Currently on antibiotic treatment for UTI, at the time of screening .
6. Able and willing to comply with the restrictions defined for the study period (see Section 10.6).

---

 The intake of IP must be started during or within five days from stop of current antibiotic treatment for UTI.

7. Access to Bank ID and ability to use the e-health platform (i.e. Internet access).
8. Ability to understand and comply with the requirements of the study, as judged by the Investigator.

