7.2.1.2 Time to first relapse of UTI

Time to first relapse of UTI will be defined as the time from delivery of intervention (*i.e.* start of intervention) to date of first confirmed UTI ((Confirm date – Intervention date) + 1).

Subjects with no UTI will be censored at last known date within the study period.

The time to first relapse will be analysed using Cox regression analysis and presented by Kaplan-Meier graphs.

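### The SAP's 14-day new-episode rule ignores the index UTI that every woman brings into the trial, so its leftover symptoms or positive test can count as a relapse

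*SAP*

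**What the plan says.** - **Entry.** Protocol 10.4, criterion 5, requires each woman to be "Currently on antibiotic treatment for UTI, at the time of screening". Its footnote adds: "The intake of IP must be started during or within five days from stop of current antibiotic treatment for UTI". Protocol 11.5 repeats this.
- **Capture of signs.** In Protocol Table 9.1 the row "Signs of recurrent UTI" has seven marks: one at the first dose and one at each of assessments 2 to 7. The diary row is marked from Day 1, and its footnote gives its content as "Information on sexual activity and signs of recurrent UTI".
- **Confirmed UTI (SAP 4.12).** Any one of three suffices: two or more symptoms, a positive test registered at site, or a self-reported positive test. The symptoms need not be new.
- **Unique UTI (SAP 4.12).** The main condition is: "If a subject have no confirmed UTIs within 14 days prior to the current confirmed UTI".
- **Clocks.** The primary count runs for six months from the start of intervention (SAP 7.1). SAP 7.2.1.2 states: "Time to first relapse of UTI will be defined as the time from delivery of intervention", and adds one day, so an event on the delivery day has time 1.
- **Index UTI.** Protocol 12.3.5 collects UTI history to confirm eligibility. SAP 4.12 does not mention it, and neither document requires the index UTI to have resolved or sets a blanking period. The list of changes in SAP 8 adds neither.

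**The concern.** The look-back works only if the previous episode is in the data it searches. For the first study episode it is not. The index UTI, the one earlier infection that every woman is known to have, falls outside the SAP's definition of a confirmed UTI. A woman who starts product while still symptomatic and records frequency and dysuria in the diary that day meets the two-symptom criterion and has no study-confirmed UTI in the prior 14 days. She is scored as having one unique UTI and a time to first relapse of one day.

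Such an event adds one to her six-month and intervention-period counts. It replaces her true first relapse in the time-to-event analysis and makes her a relapser in both relapse proportions. Under the same rule it also stops a genuine new UTI in the next 14 days from counting. The protocol gives a reason to expect some such events: after antibiotics, "the infection is not always eradicated and bacteriuria and recurrences may persist" (Protocol 7.1).

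**Working it through.** **Inputs from the documents.** Means 0.75 and 1.35 over six months, SD 1.15, 118 evaluable, power 80%, 15% drop-out, 140 included (Protocol 16.2, SAP 3.4); two-sided 5% (Protocol 16.1).

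**Assumption.** A share q of women in each arm has one leftover index event counted, independently of later UTIs. The documents give no value; 10, 20 and 30% are used for illustration.

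**1. The plan's own figure.** A two-sample t-test with 59 per arm has noncentrality 0.60 / (1.15 × √(2/59)) = 2.83, so power is 80.2%. That is 118 in total. 118 / 0.85 = 138.8, which the plan states as 140. The sample-size arithmetic is sound.

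**2. Six-month count.** Both means rise by q: (1.35 + q) − (0.75 + q) = 0.60. The difference is unchanged. The SD becomes √(1.15² + q(1 − q)).

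| q | Means | SD | Power, 59 per arm | Power, 70 per arm |
|---|---|---|---|---|
| 0 | 0.75 v 1.35 | 1.150 | 80.2% | 86.5% |
| 10% | 0.85 v 1.45 | 1.188 | 77.6% | 84.3% |
| 20% | 0.95 v 1.55 | 1.218 | 75.6% | 82.5% |
| 30% | 1.05 v 1.65 | 1.238 | 74.2% | 81.3% |

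At q = 5%, power at 59 per arm is 78.8%.

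**3. Relapse proportions.** Assume Poisson counts with half of the six-month mean falling in three months. Then P(at least one) = 1 − (1 − q)e^(−m), with m = 0.375 v 0.675 at three months and 0.75 v 1.35 at six. The difference between arms is therefore multiplied by (1 − q).

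| q | Three months | Difference (points) | Power, 59 per arm | Six months | Power, 59 per arm |
|---|---|---|---|---|---|
| 0 | 31.3% v 49.1% | 17.8 | 50% | 52.8% v 74.1% | 67% |
| 10% | 38.1% v 54.2% | 16.0 | 41% | 57.5% v 76.7% | 60% |
| 20% | 45.0% v 59.3% | 14.3 | 34% | 62.2% v 79.3% | 53% |
| 30% | 51.9% v 64.4% | 12.5 | 28% | 66.9% v 81.9% | 46% |

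**4. Time to first relapse.** Simulated with constant hazards of 0.75 and 1.35 per 180 days and leftover events spread over Days 1 to 7. Without leftovers the hazard ratio is 0.75 / 1.35 = 0.56. With q = 10, 20 and 30% it becomes about 0.61, 0.66 and 0.71; smaller runs differ by 0.01 to 0.02. Log-rank power at 59 per arm (1,500 simulated trials) falls from about 71% to 60, 47 and 38%.

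**5. Follow-up-period count.** Leftovers arise in the first days, so the count for months four to six is essentially unaffected.

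**The case against.** - **The primary result is not biased.** This stands. A reader might infer that every efficacy result is pulled toward no difference. The planned primary estimate is a difference in LSMeans, and equal leftovers leave it at 0.60. A rate ratio would shrink, but the plan does not estimate one. Nor is there bias when the product has no effect.
- **The power loss is modest and may be absorbed.** This stands in part. Protocol 10.3 and SAP 4.1 ask for 140 completed women. With 70 per arm, power stays above 81% even at q = 30%. Protocol 16.2 and SAP 3.4 instead treat 140 as the number included, with 118 evaluable. The source of the planning means is not given, so they may already contain such events.
- **Few leftovers may be captured.** This stands as a limit on size. Pre-screening, consent, randomization and pick-up come before the first dose, so treatment may be well advanced by Day 1, and the first monthly assessment is Day 30 ± 7. Early leftovers can enter only through the first-dose record, the diary or a self-reported test. Those routes are in the plan.
- **The two-week spacing is an eligibility rule.** This stands. A reader might infer that SAP 4.12 contradicts the protocol, which defines past episodes "with a minimum period of two weeks between episodes". That wording governs history at entry, with an exception for culture-proven different pathogens. The SAP is silent on the index UTI; it does not break a stated endpoint rule.
- **Early relapse may be preventable.** This stands as a caution. A reader might infer that the product could not affect these events. The documents do not separate leftover symptoms from early relapse of the index infection, and a blanking window removes both.

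**Conclusion.** The gap is real. The unique-UTI rule as written scores leftover index symptoms or a leftover positive test as a new episode, and nothing else in the documents prevents it. The effect differs by endpoint. The primary mean difference is unbiased and loses 3 to 6 points of power at 59 per arm for q between 10 and 30%. Time to first relapse and both relapse proportions are diluted toward no difference, because a leftover replaces the true first event. The intervention-period count gains noise, and the follow-up-period count is essentially unaffected.

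These sizes rest on an assumed q that is equal in both arms and independent of later UTIs, and on Poisson counts and constant hazards for the secondary endpoints. How often leftovers occur cannot be derived from the documents. The point should be fixed, mainly for the relapse endpoints; it does not put the validity of the primary test in question.

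**What to change.** - In SAP 4.12, enter the index UTI as each woman's first prior UTI in the 14-day look-back, dated at the stop of the index antibiotic course in the medication records. Apply this to the six-month count, the intervention-period count, time to first relapse and both relapse proportions.
- In the Cox analysis, keep the clock at delivery but let a woman enter the risk set only when her look-back has ended (delayed entry). Otherwise each woman has a stretch of follow-up at risk in which no event can count.
- Report a sensitivity analysis that counts all events from Day 1 as now written. SAP 7.1.2 and 7.2.4, which rule out sensitivity analyses, need a matching edit. Settle all this before the unblinded analysis.

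**Cost.** A few sentences in the SAP and a short derivation. No new data should be needed: the five-day start rule cannot be checked without the stop date, and Protocol 10.6.2 asks for the duration of antibiotic use. Neither document says outright that the stop date is recorded, so confirm it.

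**Downside.** A true early relapse or reinfection inside the window is not counted in the main analysis. Because the window is dated from antibiotic stop, it is somewhat longer than for later episodes, which are dated at the event or contact. The sensitivity analysis shows how much this matters.
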